The overall objective is to identify whether n-3 fatty acids are anti-inflammatory in both normal weight and obese subjects.

The specific objectives are:

1. To follow the appearance of inflammatory mediators in the bloodstream of normal weight and obese subjects over 6 hours following consumption of a standard high fat meal and of the same meal consumed in conjunction with capsules providing EPA+DHA.

- 2. To identify the concentrations of inflammatory mediators in the bloodstream of normal weight and obese subjects before and after 12 weeks of consumption of capsules providing EPA+DHA or placebo.
- 3. To identify the presence of inflammatory cells and expression of inflammatory genes and proteins in adipose tissue of normal weight and obese subjects before and after 12 weeks of consumption of capsules providing EPA+DHA or placebo.
- 4. To follow the appearance of inflammatory mediators in the bloodstream of normal weight and obese subjects who have been consuming n-3 fatty acids or placebo for 12 weeks over 6 hours following consumption of a standard high fat meal.

The questions being addressed by this study are:

- 1. Is the post-prandial inflammatory response different in obesity?
- 2. Can consuming marine n-3 fatty acids with a meal alter the post-prandial inflammatory response to that meal?
- 3. Is the chronic effect of marine n-3 fatty acids on inflammation different between normal weight and obese subjects?
- 4. Can marine n-3 fatty acids reduce inflammation within adipose tissue?
- 5. Does chronic use of marine n-3 fatty acids alter the post-prandial inflammatory response?

9. The study

General approach to be taken

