We will recruit normal weight and obese subjects. For the purpose of this study obesity will be defined as a body mass index (BMI) > 30 kg/m^2 and a waist circumference $\geq 94 \text{ cm}$ for men and $\geq 80 \text{ cm}$ for women. Subjects' post-prandial inflammatory response to a high fat meal and to n-3 fatty acids taken with that meal will be assessed using approaches we have used previously to study acute lipid metabolism and fatty acid appearance in the bloodstream [8,9]. Blood will be taken at several time points during the meal challenge (0, 1, 2, 3, 4 and 6 hours). Each subject will undergo both meal challenges, in random order and separated by at least 2 weeks. Subjects will then be randomised to consume placebo or "fish oil" capsules daily for about 12 weeks. Inflammatory mediators in the bloodstream will be measured at the start and end of this period. Subjects will then repeat the standard meal challenge. A range of inflammatory mediators will be measured in the blood samples. In addition, fatty acid status will be measured in all samples. An adipose tissue biopsy will be taken at study entry and after the 12 week intervention period; this will be used to assess inflammatory cell infiltrate and the levels of genes and proteins involved in inflammation.

Subjects and supplements

Subjects aged 18 to 65 years with normal weight (a body mass index (BMI) between 18.5 and 25 kg/m² (n = 50)) and obesity (BMI 30 to 40 kg/m^2 (n = 50) and a waist circumference $\geq 94 \text{ cm}$ for men and $\geq 80 \text{ cm}$ for women) will be recruited. Subjects will recruited via posters and email shots in the University of Southampton, Southampton General Hospital, and other organisations with which the researchers have contact; and via advertisements in local media including newspapers and radio. Subjects who express an interest will be screened by telephone interview. If they fit the inclusion and exclusion criteria (see below) they will be sent the information sheet. They will be contacted about 7 days later to confirm their interest or not, and if they remain interested an appointment will be made for them to visit the Wellcome Trust Clinical Research Facility at Southampton General Hospital. At this first visit the study will be explained, any questions answered and written consent obtained. Subjects will later make three clinic visits.

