Subjects who express an interest will be screened by telephone interview. If they fit the inclusion and exclusion criteria they will be sent the information sheet. They will be contacted about 7 days later to confirm their interest or not and if they remain interested an appointment will be made for them to visit the Wellcome Trust Clinical Research Facility, Southampton General Hospital. At this first visit the study will be explained, any questions answered and written consent obtained; subjects will then have height, weight, waist and hip circumference, and body composition (bioelectrical impedance) measured to confirm that they meet the inclusion criteria. A 9 ml blood sample will be taken for preparation of DNA. An appointment will be made for the first clinic visit; subsequently two further clinic visits will be made (i.e. three clinic visits in total after the initial "consenting" visit). Subjects will attend each of these three clinic visits in the fasted state (no food or drink except water after 9 pm the previous evening).

Subjects will visit the Wellcome Trust Clinical Research Facility, Southampton General Hospital on three occasions each between 8 and 10 am. On each occasion they will be in the fasted state. At each clinic visit weight, waist and hip circumference, and body composition (bioelectrical impedance) will be measured. Two visits will be for post-prandial study days prior to entering the chronic phase of the study. The third visit will be at the end of the chronic phase of the study, at which time a further post-prandial study day will occur. An adipose tissue biopsy will be taken from the subcutaneous abdominal area at the first and third clinic visits.

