Blood collected at study entry will be used to prepare DNA which will be stored and used later to seek to identify genetic factors (for example polymorphisms in genes related to lipid metabolism or inflammation) that might explain differences among individuals seen in the study. Adipose tissue biopsy material will be stored frozen at minus 80°C. Blood will be used to prepare plasma, mononuclear cells and red cells. Plasma will be aliquoted and frozen at minus 80°C. Mononuclear cells and red cells will be frozen at minus 80°C. Lipid will be extracted from plasma and red cells using chloroform/methanol and fatty acid composition determined using standard techniques. Inflammatory proteins in plasma will be measured by flow cytometry and ELISA. Lipid mediators of inflammation will be measured by mass spectrometry. Inflammatory proteins on the surface of mononuclear cells will be determined by flow cytometry. Inflammatory genes and proteins within mononuclear cells and adipose tissue will be determined by immunohistochemistry.

Data will be compared across time and between groups by ANOVA with repeated measures.

10. Data handling and record keeping

- All data will be entered onto a spreadsheet (Microsoft Excel) by the researchers involved.
- All data will be entered on a password-protected computer. This data will be accessed only by the PI and the researchers involved.
- All data will only be linked to study codes and thus not identifiable with the source volunteer. However, the caveat to this will be a data set recording the volunteer name and study code without any other volunteer details.
- All data recorded on paper will be kept in a locked filing cabinet in the researchers' office and/or in a dedicated, restricted access, clinical data storage area on Level D of the IDS Building, University of Southampton.
- Data of an identifiable nature (i.e. volunteer names, contact details, addresses) will be destroyed 12 months after the end of the study. All other data will be kept securely for 15 years and then destroyed.
- Data will be obtained, handled and stored in adherence to the principle set out in the Data Protection Act 1998.
- The investigators will permit monitoring, audits, REC and MHRA review (as applicable) and provide direct access to source data and documents.

11. Statistical Analysis

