The statistical analysis will involve the comparison of inflammatory markers (proteins, lipids etc) and of fatty acids between normal weight and obese subjects and between placebo and n-3 fatty acid treatments. All statistical comparisons will be performed at the end of the study using SPSS version 14.

12. Sample size calculation

Sample size is calculated based upon the chronic intervention phase of the study. We have considered the typical means and standard deviations of prototypical inflammatory mediators (such as interleukin-6) that we have measured previously and an anticipated 20% reduction in these concentrations by n-3 fatty acids. A sample size of 20 subjects per treatment group (i.e. placebo; n-3 fatty acid) will be required to detect a 20% difference in inflammatory markers with 80% power at the 5% significance level (p < 0.05). This number is also consistent with the number of subjects studied by others in investigations of post-prandial inflammation [7,8]. Thus, 40 normal weight and 40 obese subjects will be required to be recruited to satisfy the sample size calculation for the chronic phase of the study. To allow for a 20% drop out rate, 50 normal weight and 50 obese subjects will be recruited.

13. Safety assessments

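### Repeated-measures ANOVA, the only method the protocol names, gives a valid but less precise test of the randomised 12-week effect than adjusting for the baseline already collected

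*Protocol*

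**What the plan says.** The last line of the Sample analysis part of section 9 reads "Data will be compared across time and between groups by ANOVA with repeated measures". No other analysis method appears in the protocol. Section 11 adds the comparisons to be made, "between normal weight and obese subjects and between placebo and n-3 fatty acid treatments", and the software, but no model and no covariate. Baseline adjustment is not mentioned anywhere.

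The 12-week question is objective 2 in section 8: mediators in blood "before and after 12 weeks of consumption of capsules providing EPA+DHA or placebo". Objective 3 asks the same of adipose tissue. On the blood measurements, the General approach part of section 9 says "Inflammatory mediators in the bloodstream will be measured at the start and end of this period". The Subject participation schedule adds that "Two visits will be for post-prandial study days prior to entering the chronic phase of the study". The visit table lists blood for inflammatory markers at all three clinic visits, and a fasting zero-time sample is drawn at each. Biopsies are taken at clinic visits 1 and 3 only.

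Section 12 makes the 12-week phase the basis of the design: "Sample size is calculated based upon the chronic intervention phase of the study".

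**The concern.** The generic sentence in section 9 also covers the comparison on which the study is sized. Applied to a start value and an end value in two randomised arms, repeated-measures ANOVA treats the baseline as a second outcome. Its group-by-time term is then the difference in mean change, which fixes the coefficient of the baseline at 1. ANCOVA estimates that coefficient from the data, and under randomisation its variance is lower whenever the correlation is below 1. With about 20 completers per arm in each BMI group, the difference can matter, and the values needed for the adjustment are already being collected.

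**Working it through.** **Inputs from the protocol (section 12).** 20 subjects per treatment group within each weight group, a 20% difference, 80% power and a 5% level (two-sided assumed). The effect is "an anticipated 20% reduction in these concentrations by n-3 fatty acids".

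**Inputs not in the protocol.** The SD, and the correlation r between baseline and week-12 values. The SD is back-solved below; r is taken as 0.3, 0.5 and 0.7.

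**The protocol's own figure.** The 20 per group cannot be reproduced independently because no SD is given. Solving the two-sample t test for 20 per group and 80% power gives a standardised effect d of 0.909, so the implied SD is 20% / 0.909 = 22.0% of the mean. (The normal approximation gives 0.886 and 22.6%.) The dropout step does reproduce: 40 / (1 − 0.20) = 50 per weight group.

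**Variance of the treatment contrast**, in units of the single-visit variance, with equal variances at both times:
- group-by-time test (change score): 2(1 − r)
- ANCOVA on one baseline: 1 − r²
- ratio, ANCOVA to change score: (1 − r²) / [2(1 − r)] = (1 + r)/2

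**Power at 20 per arm** (noncentral t, two-sided 5%, d = 0.909 on the single-visit SD):

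| r | Change score: variance | ANCOVA: variance | Reduction | Power, change score | Power, ANCOVA |
|---|---|---|---|---|---|
| 0.3 | 1.40 | 0.91 | 35% | 66% | 84% |
| 0.5 | 1.00 | 0.75 | 25% | 80% | 90% |
| 0.7 | 0.60 | 0.51 | 15% | 95% | 97.5% |

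The numbers per arm needed for 80% power (normal approximation) are 28 against 19, 20 against 15, and 12 against 11. A simulation of 4,000 trials per setting, run with the slightly smaller d of 0.886, gave 63.9% against 81.4%, 77.0% against 87.2%, and 94.1% against 96.5%. Below r = 0.5, 2(1 − r) exceeds 1, so the change score is also less precise than comparing the week-12 values alone.

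**If the SD behind section 12 was already that of the change**, the group-by-time test has 80% power at every r. The variance ratio is the same, and ANCOVA then has about 93%, 90% and 86% at r = 0.3, 0.5 and 0.7.

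**Two baselines, like for like.** Assume the same correlation between all visits and use the mean of the two fasting pre-treatment values in both methods. The change-score variance is 1.5(1 − r) and the ANCOVA variance is 1 − 2r²/(1 + r):
- r = 0.3: 1.05 against 0.862, 18% lower; power 78% against 85%
- r = 0.5: 0.75 against 0.667, 11% lower; power 90% against 93%
- r = 0.7: 0.45 against 0.424, 6% lower; power 98.7% against 99.0%

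**The case against.** The best defence is that nothing here is an error. Under randomisation the group-by-time test is unbiased and has its nominal level. The sentence is a general closing line that also serves the 0 to 6 hour meal series, where repeated measures is natural, and covariates are often left to the analysis plan. The first part stands: the loss is one of efficiency only. The second part stands only in part. The protocol names a method for all its data and names no other, so improving that choice is more than asking for a missing detail.

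The power figures are also open to challenge, since r is assumed and section 12 does not say which SD was used. That stands for the power figures. It does not touch the ratio (1 + r)/2, which holds under equal variances at the two times whatever the effect size.

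Three stronger readings are tempting, and the protocol does not support them:
- A reader might infer that the group main effect, which averages in pre-treatment values and so halves the effect, will be reported as the n-3 effect, or that a change over time within one arm will be. Neither is stated. The sentence joins time and group, and section 11 specifies placebo against n-3.
- A reader might infer that the clinic visit 1 fasting sample will be ignored because section 9 speaks of the start of the period. That wording does not exclude it, and the visit table lists marker blood at both pre-treatment visits.
- A reader might credit ANCOVA with the whole gain from two-baseline ANCOVA over change from one baseline. That mixes the benefit of a second sample with the benefit of the method; the like-for-like gain is 18%, 11% or 6%.

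**Conclusion.** The concern holds as a matter of efficiency. For the randomised 12-week comparison the named method leads to a change-score test that is valid but less precise than baseline-adjusted ANCOVA. With one baseline the variance could be 35%, 25% or 15% lower at r = 0.3, 0.5 or 0.7; at r = 0.8 the gain falls to 10%.

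The gain in power matters most if r is low. At r = 0.3, and with the implied effect on the cross-sectional SD, the change-score test falls to about 66% within each BMI group while ANCOVA stays above the 80% target. At r = 0.7 both exceed 95% and the choice matters little. These figures rest on an assumed r, a back-solved effect size, equal variances at the two times and 20 completers per arm.

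The argument applies to placebo against n-3, which is randomised. It does not carry over to normal weight against obese, which is not. The change is an improvement at almost no cost, not the repair of an invalid analysis.

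**What to change.** For the chronic phase, state that the week-12 fasting value is compared between the randomised arms by ANCOVA with the pre-treatment fasting value as covariate, preferably the mean of the zero-time values at clinic visits 1 and 2. Include BMI group and a treatment-by-BMI-group term, and report the treatment effect within each BMI group. A model adjusted for BMI group alone would not answer question 3 in section 8, which asks whether the chronic effect differs between normal weight and obese subjects. Use the same form for the adipose markers, with the single baseline biopsy as covariate. Keep repeated measures for the 0 to 6 hour meal series. The protocol gives no basis for choosing a transformation, so the scale of analysis should be settled separately.

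The cost is a few lines in the protocol, carried into the analysis plan. No visit, sample or assay is added.

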The n-3 fatty acid preparation to be used is commercially available as a supplement and will be provided in capsules. Approximately 1.8 g EPA plus DHA will be given during the meal challenge and then will be given per day during the chronic phase of the study. This dose of n-3 fatty acids is similar to that used in many previous studies and is an amount consistent with the Government's

guideline range for oily fish consumption [3]. The placebo capsules will be identical in size and appearance to the fish oil capsules and will contain vegetable oil. Subjects, researchers and clinical staff will be blinded to group allocation.

Inclusion criteria

- 1. Male or female
- 2. Aged 18 to 65 years
- 3. Body mass index 18.5 to 25 or 30 to 40 kg/m^2
- 4. If body mass index is 30 to 40 kg/m² waist circumference is ≥ 94 cm for men or ≥ 80 cm for women
- 5. Not consuming fish oil or other oil supplements
- 6. Not eating more than one oily fish meal per week
- 7. Willing to adhere to the study protocol
- 8. Being able to provide written informed consent

[figure not shown]
Exclusion criteria

- 1. Aged < 18 or > 65 years
- 2. Body mass index $< 18.5, 25-29.9 \text{ or } > 40 \text{ kg/m}^2$
- 3. If body mass index is 30 to 40 kg/m^2 waist circumference is < 94 cm for men or < 80 cm for women
- 4. Diagnosed diabetes
- 5. Use of prescribed medicine to control inflammation
- 6. Use of prescribed medication to control blood lipids (e.g. statins, fibrates (fenofibrate), Omacor)
- 7. Use of prescribed medication to control blood pressure (ACE inhibitors, angiotensin 2 receptor blockers, calcium channel blockers, α-inhibitors, thiozide diuretics)
- 8. Use of fish oil or other oil supplements
- 9. Chronic gastrointestinal problems (e.g. IBD, celiac disease, cancer)
- 10. Pregnant or planning to become pregnant within the study period
- 11. Participation in another clinical trial

Subject participation schedule

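### The obese versus normal-weight contrast is not randomised, and the protocol names neither age and sex balancing nor adjustment for it

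*Protocol*

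**What the plan says.** Section 8 lists as Question 1: "Is the post-prandial inflammatory response different in obesity". Question 3 uses the same two groups in another way: "Is the chronic effect of marine n-3 fatty acids on inflammation different between normal weight and obese subjects".

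What is randomised is set out in section 9, General approach: the order of the two meal challenges, and then the capsules ("Subjects will then be randomised to consume placebo or" fish oil). BMI group is a recruitment stratum. Under Subjects and supplements, one age range covers both strata ("Subjects aged 18 to 65 years with normal weight" or obesity), and the first inclusion criterion is "Male or female". The strata have fixed sizes, BMI limits and, for the obese group, waist limits. There is no age band, sex quota or matching rule.

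On analysis, section 9 (Sample analysis) states: "Data will be compared across time and between groups by ANOVA with repeated measures". Section 11 plans a "comparison of inflammatory markers (proteins, lipids etc) and of fatty acids between normal weight and obese subjects" and, in the same sentence, the comparison of placebo with n-3. It then adds only the timing and the software. Neither section names a covariate or says that covariates are excluded.

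**The concern.** One method is stated for two contrasts that have different protection. Randomisation balances age and sex in expectation between placebo and n-3. Nothing does so between obese and normal-weight volunteers, and with an eligible range of 18 to 65 years and both sexes there is ample room for the strata to differ.

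If they do differ, and if age or sex is related to a marker or to its post-prandial course, the group term in the ANOVA contains that relation as well as any relation with obesity. Question 1 rests wholly on this contrast, so a difference put down to obesity could be partly one of age or sex.

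**Working it through.** **Which questions are exposed**

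- *Question 1.* It compares the BMI groups directly, so it is exposed both to a relation of age or sex with marker level and to one with the post-prandial response.
- *Question 3.* It compares the n-3 effect between BMI groups. Treatment is randomised, so main effects of age and sex drop out of the n-3 contrast within each group. The comparison is distorted only if age or sex modifies the n-3 effect.
- *n-3 versus placebo within a BMI group.* Randomised, so not affected.

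**Group sizes (section 12)**

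Two treatment groups of 20 give 2 × 20 = 40 per BMI group, and 40 / 0.8 = 50 with 20% dropout. Both figures reproduce. They were derived for the n-3 effect; the protocol gives no target difference for obese versus normal weight. No standard deviation is given, so a bias can be expressed only in SD units.

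**Illustration of size**

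Let d be the difference in a covariate (say age) between BMI groups, in within-group SDs, and r its within-group correlation with the outcome analysed. With no true obesity difference:

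- bias = r × d, in SDs of the outcome;
- rejection probability = that of a two-sided 5% t test with 2n − 2 degrees of freedom and noncentrality r × d × √(n/2).

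The values of r and d are assumptions; neither is in the protocol.

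| r | d | Bias (SD) | Rejection, n = 40 per group | Rejection, n = 50 per group |
|---|---|---|---|---|
| 0.1 | 0.25 | 0.025 | 5.1% | 5.2% |
| 0.2 | 0.5 | 0.10 | 7.3% | 7.9% |
| 0.3 | 0.5 | 0.15 | 10.2% | 11.5% |
| 0.3 | 1.0 | 0.30 | 26.3% | 31.8% |

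For example, in the last row with n = 40, the noncentrality is 0.30 × √20 = 1.34. For Question 1, r must be the correlation with the response over 0 to 6 hours, which may be weaker than that with the fasting level.

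**Cost of adjusting**

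With 80 subjects in two BMI groups there are 80 − 2 = 78 between-subject residual degrees of freedom; age and sex use two, leaving 76. If the four BMI-by-treatment cells are modelled, 80 − 4 = 76 falls to 74.

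An imbalance also has a price in precision. For one covariate and equal groups, the variance of the adjusted contrast relative to the unadjusted one is (1 + d²/4) × (1 − r²).

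- r = 0.3, d = 0.5: 1.0625 × 0.91 = 0.97, a slight gain.
- r = 0.3, d = 1.0: 1.25 × 0.91 = 1.14, or about 7% on the standard error (√1.14 = 1.07).

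**The case against.** The strongest objection is that this is drawn from silence. A covariate list is commonly left to the SAP, which may exist and is not shown, and a repeated-measures ANOVA can carry covariates. That much stands: a reader might infer that the protocol prescribes an unadjusted comparison, and it does not say so. What remains is that the protocol itself fixes the recruitment design, without any age or sex balancing, and names the analysis method, without separating the non-randomised contrast from the randomised one. An SAP could add covariates, but it cannot restore overlap if the two age distributions hardly meet.

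A reader might also infer from recruitment by "posters and email shots in the University of Southampton, Southampton General Hospital, and other organisations" that the lean group will be younger and campus-based. The same sentence goes on to local newspapers and radio, and the same channels serve both strata. An imbalance is possible; the protocol does not show that one will occur.

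Nor should the bias be set against the 20% in section 12. Suppose a marker rose 5 to 10% per decade and the groups were 10 to 15 years apart. The spurious difference would be 1.05^1.0 − 1 = 5% to 1.10^1.5 − 1 = 15%. Those inputs are not in the protocol, and the 20% is the anticipated n-3 effect between randomised arms. The result is also a difference in level: Question 1 concerns the response, and a proportional difference in level cancels from a relative change from baseline.

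Lastly, Question 1 is worded descriptively and claims no cause. That is fair. Reporting an association guards against a later over-reading; it corrects no statement in the protocol.

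**Conclusion.** The point holds in a limited form. The contrast behind Question 1 is not randomised, both strata span the full age range and both sexes, and the protocol names neither balancing nor adjustment. Followed as written, the analysis is open to confounding by age and sex.

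The size cannot be derived from the document. Under the assumed inputs above, with 40 per group, the false-positive rate at a nominal 5% runs from 5.1% to 26.3%. That range rests wholly on the chosen r and d and is an illustration, not a forecast.

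A reader might carry the concern over to Question 3 in full. The documents do not support that, since treatment is randomised and only effect modification by age or sex would matter. The randomised n-3 versus placebo comparisons, for which the trial is sized, are untouched. This is an inexpensive improvement to one study question and not a flaw in the trial's main comparison.

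**What to change.** In section 9 (Sample analysis) and section 11:

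1. State that every obese versus normal-weight comparison includes age and sex as covariates in the repeated-measures model, or refer to the SAP if it already says so. Let both covariates interact with time. The response asked about in Question 1 is a group-by-time term, and covariates entered only as between-subject main effects do not adjust it.
2. State that this contrast will be reported as an association, since other differences between volunteers may remain after adjustment.
3. For Question 3, add age-by-treatment and sex-by-treatment terms as a sensitivity analysis only.
4. Optionally, frequency-match the BMI groups on sex and broad age band while recruitment is open. This may slow recruitment a little and can be left out.

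The cost is a change of wording. Age and sex are already needed for eligibility (the age limits and the sex-specific waist limits), so no new data are collected. The main adjustment takes two between-subject degrees of freedom. The time interactions take 2 × 5 = 10 of the 78 × 5 = 390 within-subject degrees of freedom for one meal day with six time points and 80 complete subjects. The sensitivity analysis in item 3 uses two more.

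### Section 12's 80% power covers placebo v n-3 within one BMI group for one marker; question 3, a treatment x BMI-group interaction, has about 52% for a 20-point difference

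*Protocol*

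**What the plan says.** Protocol section 12 bases the sample size on the chronic phase. It gives as inputs "an anticipated 20% reduction in these concentrations by n-3 fatty acids" and says of the variability: "We have considered the typical means and standard deviations of prototypical inflammatory mediators (such as interleukin-6) that we have measured previously". No mean or SD is printed. Twenty subjects per treatment group are then "required to detect a 20% difference in inflammatory markers with 80% power at the 5% significance level". From this follow 40 normal weight and 40 obese subjects, raised to 50 and 50 for a 20% dropout, so the 20 per arm applies inside each BMI group.

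The aims are in section 8: "The overall objective is to identify whether n-3 fatty acids are anti-inflammatory in both normal weight and obese subjects". Question 3 reads: "Is the chronic effect of marine n-3 fatty acids on inflammation different between normal weight and obese subjects".

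On analysis, section 11 lists the "comparison of inflammatory markers (proteins, lipids etc) and of fatty acids between normal weight and obese subjects" and the comparison between the placebo and n-3 treatments. The sample analysis part of section 9 adds that data will be compared over time and between groups by repeated-measures ANOVA. On outcomes, the general approach in section 9 says: "A range of inflammatory mediators will be measured in the blood samples".

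**The concern.** The contrast that was sized is not the contrast that question 3 needs. Question 3 is about the difference between two treatment effects, and that difference has twice the variance of either effect alone. Section 12 gives no power for it, and neither section 9 nor section 11 commits to testing it.

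Two consequences follow. First, a reader who takes the 80% as cover for the chronic-phase aims will read a null answer to question 3 as evidence of similar effects, when the design had roughly even odds of detecting even an all-or-nothing difference of 20 points. Second, if the interaction is not tested, the easy substitute is to compare the p-value in normal weight subjects with the p-value in obese subjects. That can produce an apparent difference between the groups when none exists.

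The power and significance level are also claimed for inflammatory markers in the plural. With no primary marker, each marker tested at 5% adds another chance of a false positive.

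**Working it through.** **Inputs (Protocol section 12).** Power 80%; level 5%, sidedness not stated, taken as two-sided; effect 20%; 20 per arm within each BMI group (80 evaluable in four cells).

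**The plan's own figures.** The 20 per arm cannot be rebuilt, because no mean or SD is given. The dropout step is right: 40 / (1 − 0.20) = 50. The stated 80% is therefore taken as given. The results below do not need the missing SD, only that the 80% is true of the within-group comparison.

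**Step 1: express the claim in SD units.** For a two-sample t test with 20 per arm (df 38, two-sided 5%), 80% power corresponds to a difference of 0.909 SD, where SD is that of whatever quantity is analysed. So 20 points = 0.909 SD. The standard error of the within-group contrast is SD × √(2/20) = 0.316 SD.

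**Step 2: interaction (question 3).** The standard error of the difference between two treatment effects is SD × √(4/20) = 0.447 SD, with df 80 − 4 = 76. For a 20-point difference the noncentrality is 0.909 / 0.447 = 2.03.

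| Difference between BMI groups in the n-3 effect | Interaction power |
|---|---|
| 5 points | 7% |
| 10 points | 17% |
| 15 points | 32% |
| 20 points (20% v zero) | 52% |
| about 28 points | 80% |
| 30 points | 85% |

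The normal approximation gives 51% at 20 points, and a one-sided 5% test about 55%. For 80% power at 20 points the design would need 40 evaluable per arm in each BMI group, twice the present 20.

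**Step 3: a significant effect in both groups.** The two BMI groups are different people, so with a true 20% effect in each, joint power = 0.80 × 0.80 = 64% (about 66% with a pooled error term, df 76).

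**Step 4: comparing two p-values.** With the same true 20% effect in both groups:
- both significant: 0.80 × 0.80 = 64%
- exactly one significant: 2 × 0.80 × 0.20 = 32%
- neither significant: 0.20 × 0.20 = 4%

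So a false pattern of response in one group only would arise in about one trial in three.

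**Step 5: the pooled treatment effect, for comparison.** With 40 v 40 and a 20% effect in both groups, power is 98%. This is well powered, but it answers neither question 3 nor whether each group responds.

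**The case against.** The strongest reply is that section 12 contains no false statement. It claims 80% for neither the interaction nor a joint result. That stands: the fault is a mismatch between what was sized and what is asked, not an arithmetic error.

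It can also be said that repeated-measures ANOVA can carry a treatment x BMI-group term, that section 11 need not be a full list of model terms, and that an analysis plan not shown may settle both the model and multiplicity. This is fair, and a reader should not infer that the investigators will compare two p-values; no passage says so. But the sample size basis is fixed in the protocol, and a later plan cannot give question 3 power that the design lacks.

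Several stronger readings are tempting and are not supported:

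- *The overall objective has only 64% power.* Section 8 asks whether n-3 is anti-inflammatory in both groups, which can equally mean one answer per group, each with 80%. No success rule demands two significant tests.
- *The design works only for a marker with an SD of at most 22% of its mean.* That ceiling comes from a comparison of week-12 values alone. The plan measures before and after, and section 12 does not say which SD was used.
- *A false anti-inflammatory claim is probable, with a calculable rate.* The documents give neither the number of markers nor their correlation. The usual independence formula also counts errors in both directions, whereas such a claim needs the favourable one. Only the direction of the problem can be stated.
- *One group significant and the other not is the likely outcome under equal effects.* At 32% it is half as frequent as both significant.

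**Conclusion.** The point holds in this form: the 80% is a per-BMI-group, single-marker figure offered as the basis for the chronic phase, and question 3 has clearly less. Its power is about 52% for a full 20-point difference and 17% for 10 points; the difference detectable with 80% power, about 28 points, exceeds the whole anticipated effect of 20%.

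These figures assume that the stated 80% is correct, a two-sided 5% level, equal SDs in the two BMI groups, effects on a common percentage scale, and 20 evaluable per arm per group. The 64% applies only if significance in each group is what the objective requires. The multiplicity point is qualitative: the 5% level is attached to several markers with none named as primary.

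**What to change.** 1. In section 12, state that the 80% is per BMI group for one marker. Add the power for question 3 (about 52% at a 20-point difference) and, if a joint result is intended, 64% for a significant effect in both groups. Say which reading of the overall objective applies.
2. In section 11, specify one chronic-phase model over all randomised subjects, with treatment, BMI group, their interaction and the baseline value. Answer question 3 by the interaction estimate with its 95% CI, not by setting two p-values side by side. For the overall objective, report the treatment effect with its CI in each BMI group; a pooled effect alone would not address it.
3. Name one primary chronic-phase marker at week 12. Interleukin-6 is the only marker section 12 cites, and only as an example, so the choice is the investigators'. Treat the others as secondary with a multiplicity adjustment, or as exploratory.

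Cost: wording in the protocol and in any analysis plan, with no extra subjects. The price is a less favourable stated power for question 3 and a lower status for the remaining markers.
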